8.2. Plasma Cytokines/Chemokine Analysis

Pre-first vaccination cytokine/chemokine concentration will be determined using the mean concentrations among pre-vaccination measurements at Day -7 to -1 and Day 1. Cytokine/chemokine concentrations as well as their baseline fold changes will be summarized using minimum, Q1, median, Q3, maximum, and 95% CI of the median (starting with Table 26 and ending with Table 121). The 95% CI of the median concentration and median fold change from baseline will be determined by using the bootstrap method using 1,000 bootstrap replicates and will be visualized using time trend plots (Figure 4) and radar plots (Figure 5). To identify cytokines/chemokines that show a differential response from baseline, a two-sided Wilcoxon signed-rank test will be carried out for each study arm and post-vaccination time point (Table 122, Table 123). Significant differences in fold changes between study arms for shared post-vaccination time points will be evaluated using a Wilcoxon rank-sum test (Table 124, Table 125). Data listings of cytokine/chemokine assay results will be provided as shown in Listing 9 sorted by study group, subject ID, and visit.

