3. STUDY OBJECTIVES AND ENDPOINTS

3.1. Study Objectives

Primary Objectives

1. To assess the serum anti-HA hemagglutination-inhibition (HAI) response to influenza A/H7N9 antigen (with and without adjuvant) at Day 57 (approximately one month after the second study vaccination with A/H7N9 vaccine ± AS03) and influenza A/H3N2v antigen at Day 29 (approximately one month after the study vaccination with A/H3N2v vaccine).
2. To identify differentially expressed genes in human immune cells on Days 2, 4, and 29 (following the first study vaccination with A/H7N9 vaccine ± AS03) and on Days 30, 32, and 36 (following the second study vaccination with A/H7N9 vaccine ± AS03), compared to baseline assessments performed prior to each study vaccination (Days -7, 1, and 29).

Secondary Objectives

1. To compare plasma cytokine and chemokine profiles at specific time points and between treatment arms:
 - a. Post-vaccination time points [(Days 2 and 4; Day 8 (A/H3N2v arm only)], and Days 30, 32, and 36 (A/H7N9 arms only) with pre-vaccination time points (Days -7 and 1, prior to first study vaccination and Day 29, prior to second study vaccination (A/H7N9 arms only).
2. To assess the neutralizing antibody responses to influenza A/H7N9 antigen (with and without adjuvant) at Day 57 (approximately one month after the second study vaccination with A/H7N9 vaccine ± AS03) and influenza A/H3N2v antigen at Day 29 (approximately one month after the study vaccination with A/H3N2v vaccine).
3. To identify differentially expressed genes in human immune cells on Days 2, 4, and 8 following one intramuscular dose of influenza A/H3N2v vaccine compared to baseline assessments performed prior to study vaccination (Day -7 and Day 1).

Tertiary Objectives

1. To assess the frequency of adverse events.
2. To identify differentially abundant cellular proteins in human immune cells on Days 2, 4, and 8 following one intramuscular dose of influenza A/H3N2v vaccine compared to baseline assessments performed prior to study vaccination (Day -7 and Day 1).
3. To identify differentially abundant cellular proteins in human immune cells on Days 2, 4, and 29 (following first study vaccination with A/H7N9 vaccine ± AS03) and Days 30, 32, and 36 (following second study vaccination with A/H7N9 vaccine ± AS03), compared to baseline assessments performed prior to study vaccination (Days -7, 1, and 29).

Exploratory Objectives

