4.5.1. Immunogenicity Variables

Venous blood samples (approximately 10 mL) for HAI and Neut antibody assays were collected from subjects at Day 1 (immediately prior to the first study vaccination), and at approximately Days 29 (for A/H7N9-vaccinated subjects this was collected immediately prior to the second study vaccination) and 57 (A/H7N9-vaccinated subjects only) after the first study vaccination. Subjects who withdrew early had HAI and Neut antibody assays run on available sera, including sera from the early termination visit, if available.

Individual HAI and Neut results will be reported by the central immunology laboratory for the A/Shanghai/02/2013xPR8 vaccine strain and the A/Minnesota/11/2010 vaccine strain for the A/H3N2v study arm. Assay results will be reported as a reciprocal titer with values of $10 \cdot 2^k$, where $k=0, 1, 2$, etc. The lower limit of detection for the HAI and Neut assays is 1:10; values below the limit of detection will be imputed for analysis using one-half the limit of detection ($10/2 = 5$). For analysis, the geometric mean (calculated on natural log scale) of repeated results for each sample will be computed and used as the response for all subsequent calculations. The variation arising from multiple measurements for an individual at a single time point will not be used in subsequent calculations/statistics. See Section 3.3 for definitions of derived variables for the analysis of HAI and Neut data.

Cytokine and chemokine levels in plasma obtained from venous blood samples were quantitatively measured at approximately Days -7, 1, 2, 4, and 8 (A/H3N2v-vaccinated subjects only) and at approximately Days 29, 30, 32, and 36 for A/H7N9-vaccinated subjects only using the Luminex platform. Cytokine and chemokine levels will be reported as concentrations. Values below the plate-specific LOD for each cytokine and chemokine will be imputed using 1/2 LOD.

4.5.2. -Omics Variables

Transcriptome profiling using RNA-Seq was performed on immune cell subsets collected at approximately Days -7, 1, 2, 4, and 8 (A/H3N2v-vaccinated subjects only) and at approximately Days 29, 30, 32, and 36 for A/H7N9-vaccinated subjects only. Total RNA was isolated using standard methods and subjected to ultra-

high-throughput parallel next generation sequencing. Gene expression levels for each gene were estimated based on the number of mapping sequencing reads.

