6.8. Multiple Comparisons/Multiplicity

No multiple testing adjustments will be carried out for the safety, immunogenicity, and cytokine/chemokine endpoints. For -omics endpoints, the false-discovery rates (FDR) based on the Benjamini-Hochberg procedure as implemented in the R *p.adjust* function will be used to control the false positive rate among significantly differentially expressed genes, proteins, and enriched pathways.

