Table 120: Interferon-Beta Fold Change by Study Visit Day and Treatment Group in the Intent-To-Treat Population

Table 121: Interferon-Beta Fold Change by Study Visit Day and Treatment Group in the Per-Protocol Population

Table 122: Wilcoxon Signed-Rank Test Results for Comparing Cytokine/Chemokine Concentrations between Pre- and Post-Vaccination Time Points in the Intent-To-Treat Population

		Study Arm 1 A/H3N2v, D1 (N=X)	Study Arm 2 A/H7N9 + AS03, D1, 29 (N=X)	Study Arm 3 A/H7N9 + PBS, D1, 29 (N=X)
Cytokine	Comparison	Wilcoxon Statistic (P-value)	Wilcoxon Statistic (P-value)	Wilcoxon Statistic (P-value)
Fractalkine	Day 2 (Post -Vaccination 1) vs. Pre-Vaccination 1	x xxx (x xxx)	x xxx (x xxx)	x.xxx (x xxx)
Fractalkine	Day 4 (Post-Vaccination 1) vs. Pre-Vaccination 1	x xxx (x.xxx)	x xxx (x xxx)	x.xxx (x xxx)
Fractalkine	Day 8 (Post-Vaccination 1) vs. Pre-Vaccination 1	x xxx (x.xxx)	n/a	n/a
Fractalkine	Day 29 (Post-Vaccination 1) vs. Pre-Vaccination 1	n/a	x xxx (x xxx)	x.xxx (x xxx)
Fractalkine	Day 2 (Post-Vaccination 2) vs. Pre-Vaccination 2	n/a	x xxx (x xxx)	x.xxx (x xxx)
Fractalkine	Day 4 (Post-Vaccination 2) vs. Pre-Vaccination 2	n/a	x xxx (x xxx)	x.xxx (x xxx)
Fractalkine	Day 8 (Post-Vaccination 2) vs. Pre-Vaccination 2	n/a	x xxx (x xxx)	x.xxx (x xxx)
GM-CSF	Day 2 (Post -Vaccination 1) vs. Pre-Vaccination 1	x xxx (x xxx)	x xxx (x xxx)	x.xxx (x xxx)
GM-CSF	Day 4 (Post-Vaccination 1) vs. Pre-Vaccination 1	x xxx (x.xxx)	x xxx (x xxx)	x.xxx (x xxx)
GM-CSF	Day 8 (Post-Vaccination 1) vs. Pre-Vaccination 1	x xxx (x.xxx)	n/a	n/a
GM-CSF	Day 29 (Post-Vaccination 1) vs. Pre-Vaccination 1	n/a	x xxx (x xxx)	x.xxx (x xxx)
GM-CSF	Day 2 (Post-Vaccination 2) vs. Pre-Vaccination 2	n/a	x xxx (x xxx)	x.xxx (x xxx)
GM-CSF	Day 4 (Post-Vaccination 2) vs. Pre-Vaccination 2	n/a	x xxx (x xxx)	x.xxx (x xxx)
GM-CSF	Day 8 (Post-Vaccination 2) vs. Pre-Vaccination 2	n/a	x xxx (x xxx)	x.xxx (x xxx)
Interferon-gamma	Day 2 (Post -Vaccination 1) vs. Pre-Vaccination 1	x xxx (x xxx)	x xxx (x xxx)	x.xxx (x xxx)
Interferon-gamma	Day 4 (Post-Vaccination 1) vs. Pre-Vaccination 1	x xxx (x.xxx)	x xxx (x xxx)	x.xxx (x xxx)
Interferon-gamma	Day 8 (Post-Vaccination 1) vs. Pre-Vaccination 1	x xxx (x.xxx)	n/a	n/a
Interferon-gamma	Day 29 (Post-Vaccination 1) vs. Pre-Vaccination 1	n/a	x xxx (x xxx)	x.xxx (x xxx)
Interferon-gamma	Day 2 (Post-Vaccination 2) vs. Pre-Vaccination 2	n/a	x xxx (x xxx)	x.xxx (x xxx)

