Interferon-gamma	Day 4 (Post-Vaccination 2) vs. Pre-Vaccination 2	n/a	x xxx (x xxx)	x.xxx (x xxx)
Interferon-gamma	Day 8 (Post-Vaccination 2) vs. Pre-Vaccination 2	n/a	x xxx (x xxx)	x.xxx (x xxx)

Colored in blue= p-value < 0.05

Continue for the remaining cytokine/chemokines IL-1b, IL-2, IL-4, IL-5, IL-6, IL-7, IL-8, IL-10, IL-12p70, IL-13, IL-17A, IL-21, IL-23, ITAC, MIP 1a, MIP1b, MIP3a, TNF-alpha, IP-10, IFNa, IFNb

Table with similar format:

Table 123: Wilcoxon Signed-Rank Test Results for Comparing Cytokine/Chemokine Concentrations between Pre- and Post-Vaccination Time Points in the Per-Protocol Population

Table 124: Wilcoxon Rank Sum Test Results for Comparing Fold Changes between Study Groups in the Intent-To-Treat Population

		Study Arm 2 A/H7N9 + AS03, D1, 29 (N=X) vs. Study Arm 3 A/H7N9 + PBS, D1, 29 (N=X)	Study Arm 2 A/H7N9 + AS03, D1, 29 (N=X) vs. Study Arm 1 A/H3N2v, D1 (N=X)	Study Arm 3 A/H7N9 + PBS, D1, 29 (N=X) vs. Study Arm 1 A/H3N2v, D1 (N=X)
Cytokine	Comparison	Wilcoxon Statistic (p-value)	Wilcoxon Statistic (p-value)	Wilcoxon Statistic (p-value)
Fractalkine	Day 2 (Post -Vaccination 1) vs. Pre-Vaccination 1	x xxx (x xxx)	x xxx (x xxx)	x.xxx (x xxx)
Fractalkine	Day 4 (Post-Vaccination 1) vs. Pre-Vaccination 1	x xxx (x xxx)	x xxx (x xxx)	x.xxx (x xxx)
Fractalkine	Day 29 (Post-Vaccination 1) vs. Pre-Vaccination 1	x xxx (x xxx)	n/a	n/a
Fractalkine	Day 2 (Post-Vaccination 2) vs. Pre-Vaccination 2	x xxx (x xxx)	n/a	n/a
Fractalkine	Day 4 (Post-Vaccination 2) vs. Pre-Vaccination 2	x xxx (x xxx)	n/a	n/a
Fractalkine	Day 8 (Post-Vaccination 2) vs. Pre-Vaccination 2	x xxx (x xxx)	n/a	n/a
GM-CSF	Day 2 (Post -Vaccination 1) vs. Pre-Vaccination 1	x xxx (x xxx)	x xxx (x xxx)	x.xxx (x xxx)
GM-CSF	Day 4 (Post-Vaccination 1) vs. Pre-Vaccination 1	x xxx (x xxx)	x xxx (x xxx)	x.xxx (x xxx)
GM-CSF	Day 29 (Post-Vaccination 1) vs. Pre-Vaccination 1	x xxx (x xxx)	n/a	n/a
GM-CSF	Day 2 (Post-Vaccination 2) vs. Pre-Vaccination 2	x xxx (x xxx)	n/a	n/a
GM-CSF	Day 4 (Post-Vaccination 2) vs. Pre-Vaccination 2	x xxx (x xxx)	n/a	n/a
GM-CSF	Day 8 (Post-Vaccination 2) vs. Pre-Vaccination 2	x xxx (x xxx)	n/a	n/a
Interferon-gamma	Day 2 (Post -Vaccination 1) vs. Pre-Vaccination 1	x xxx (x xxx)	x xxx (x xxx)	x.xxx (x xxx)
Interferon-gamma	Day 4 (Post-Vaccination 1) vs. Pre-Vaccination 1	x xxx (x xxx)	x xxx (x xxx)	x.xxx (x xxx)
Interferon-gamma	Day 29 (Post-Vaccination 1) vs. Pre-Vaccination 1	x xxx (x xxx)	n/a	n/a

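### The two-sample mean baseline for cytokines pulls the median fold change after dose 1 downward and lets within-arm tests find falls more easily than equal rises

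*SAP*

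**What the plan says.** SAP 8.2 defines the reference for all comparisons after dose 1: "Pre-first vaccination cytokine/chemokine concentration will be determined using the mean concentrations among pre-vaccination measurements at Day -7 to -1 and Day 1". The kind of mean is not named. Concentrations and fold changes "will be summarized using minimum, Q1, median, Q3, maximum, and 95% CI of the median", the last by bootstrap.

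For change from baseline, "a two-sided Wilcoxon signed-rank test will be carried out for each study arm and post-vaccination time point". The shell for Table 122 is titled "Wilcoxon Signed-Rank Test Results for Comparing Cytokine/Chemokine Concentrations between Pre- and Post-Vaccination Time Points in the Intent-To-Treat Population" and carries the footnote "Colored in blue= p-value < 0.05". SAP 6.8 adds: "No multiple testing adjustments will be carried out for the safety, immunogenicity, and cytokine/chemokine endpoints". Between-arm comparisons (Tables 124 and 125) are rank-sum tests on fold changes.

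After dose 2 the reference is one sample. SAP 3.1 names it as "Day 29, prior to second study vaccination (A/H7N9 arms only", and Table 122 labels the contrast as against Pre-Vaccination 2.

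For antibody titers, SAP 4.5.1 says that "the geometric mean (calculated on natural log scale) of repeated results for each sample will be computed", so the SAP names a geometric mean where it wants one.

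**The concern.** A fold change is a ratio, but here its numerator is one concentration and its denominator is an average of two taken on the natural scale. The arithmetic mean of two unequal positive numbers always exceeds their geometric mean. A subject who does not respond therefore has an expected log fold change below zero, and the deficit grows with visit-to-visit noise.

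Two outputs are at stake. One is the median fold change after dose 1 in Tables 74 to 121 and Figures 4 and 5. The other is the set of dose-1 within-arm tests in Tables 122 and 123, which serve secondary endpoint 1a. A rise is the likelier response of interest after vaccination, and it is the direction that the baseline works against. Dose-1 and dose-2 fold changes also appear in the same tables and plots although only the former carry the shift.

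**Working it through.** The documents give no power, bias or variability figure for cytokines, so there is no figure of the plan's own to reproduce.

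**Inputs from the documents.** Ten subjects per arm (SAP 4.1); two-sided signed-rank test flagged at 0.05 (SAP 8.2, Table 122); two-sample baseline before dose 1, one-sample baseline before dose 2.

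**Assumed inputs.** Lognormal concentrations; within-subject log SD s from 0.2 to 1.0; between-subject log SD 0.5 or 1.0; true change k-fold up or 1/k-fold down. The test is the exact signed-rank test at n = 10 (reject at W ≤ 8, exact size 0.0488), with 100,000 simulated trials per cell.

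**1. Bias in the fold change.** Let d be the difference between a subject's two baseline logs. Then log(arithmetic mean) − log(geometric mean) = log cosh(d/2). With d of variance 2s², and log cosh(x) ≈ x²/2, the expectation is about (1/2)(2s²/4) = s²/4. With no true change the median fold change should be near exp(−s²/4):

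| s | exp(−s²/4) | simulated median |
|---|---|---|
| 0.3 | 0.978 | 0.979 |
| 0.5 | 0.939 | 0.943 |
| 0.7 | 0.885 | 0.897 |
| 0.8 | 0.852 | 0.87 |
| 1.0 | 0.779 | 0.813 |

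The formula overstates the shift somewhat at larger s. By simulation the loss is about 2%, 6% and 13% at s = 0.3, 0.5 and 0.8. The direction is specific to the median or log fold change, which is what the SAP reports. The arithmetic mean of the fold changes would be shifted upward (1.14 at s = 0.5).

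**2. Source of the asymmetry.** Take one baseline sample X·e^b and one later sample. After a k-fold rise the difference is X(k·e^a − e^b). After a k-fold fall it is (X/k)(e^a − k·e^b). Since a and b are exchangeable, the second is the mirror image of the first, rescaled by 1/k, and signed ranks ignore a common rescaling. A test on concentrations is therefore symmetric when the baseline is one sample. Power at s = 0.5, k = 1.5, between-subject SD 1.0:

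| Baseline | Test scale | Rise | Fall |
|---|---|---|---|
| One sample (dose-2 design) | concentration | 30.7% | 30.3% |
| Arithmetic mean of two (plan) | concentration | 31.6% | 44.0% |
| Arithmetic mean of two | log | 34.3% | 54.6% |
| Geometric mean of two | concentration | 41.2% | 35.6% |
| Geometric mean of two | log | 44.8% | 44.8% |

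The planned version has a gap of 44.0 − 31.6 = 12.4 points. Changing only the test scale widens it to 54.6 − 34.3 = 20.3. Changing only the baseline reverses it, to 41.2 − 35.6 = 5.6 in favour of rises. Both together remove it.

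**3. False flags.** With no true change at s = 0.5, the planned test flags rises in about 1.5% of trials and falls in 3.7 to 3.8%, a total near 5.3%. At s = 1.0 the split is 1.0% and about 5.0%, a total near 6.0%. Table 122 has nine dose-1 arm-by-day cells per analyte: Days 2 and 4 in three arms (6), Day 8 in one arm (1) and Day 29 in two arms (2). With 24 analytes that is 24 × 9 = 216 tests per population. If all were null at s = 0.5, the expected flags are 216 × 0.015 ≈ 3 rises and 216 × 0.038 ≈ 8 falls.

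**4. Separate loss from the concentration scale.** With one baseline sample, between-subject SD 1.0 and a 1.5-fold rise, power is 66% on concentrations and 75% on logs at s = 0.3, and 30.7% against 35.5% at s = 0.5. Log fold change does not depend on between-subject level, but the concentration difference does, so the loss grows with between-subject spread. At s = 0.5 and between-subject SD 0.5 the concentration test reaches 32.5%. This loss is non-directional and also applies after dose 2.

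**5. Between-arm tests.** Power of the rank-sum test for a 1.5-fold difference between arms, arithmetic against geometric baseline, is 37.2% and 37.5% at s = 0.4, and 18.6% and 18.8% at s = 0.6.

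**The case against.** The strongest reply has four parts.

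- **Size.** The size is unknown because s is not in the documents. This stands: at s = 0.2 to 0.3 the shift is 1 to 2%, and it becomes material only from about 0.5.
- **Wording.** Neither arithmetic nor raw scale is written; the first is inferred from unqualified wording and the second from a table title. This also stands, but if the sponsor meant otherwise the SAP still needs a sentence saying so.
- **Consistency.** The titer rule concerns repeat assays of one sample, not two visits. A closer parallel is SAP 9.1.4, where the two RNA-Seq baselines are combined by summing read counts. That is fair. The case for change rests on the arithmetic above, not on inconsistency with the titer rule.
- **Purpose.** Protocol 11.2 describes a hypothesis-generating study, the sample size has no formal basis, and no dose-1 against dose-2 test is planned. This limits the severity but does not remove the bias.

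A reader might infer more than the documents support in three ways. First, that testing concentrations causes the rise/fall asymmetry: it does not, and under the planned baseline it partly offsets it. Second, that the adjuvant comparison is biased: the rank-sum tests of Tables 124 and 125 compare fold changes that share the same shift if within-subject variability is equal across arms. Third, that type I error is badly wrong: the total stays near nominal, and only its split between directions is distorted.

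**Conclusion.** The point holds for within-arm results after dose 1, meaning endpoint 1a and the dose-1 columns of the fold-change tables and plots. Averaging two baseline concentrations on the natural scale is the whole source of the directional bias. The concentration scale of the signed-rank test is a second, smaller matter of power. Dose-1 and dose-2 fold changes are not on the same footing descriptively.

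The conclusion rests on right-skewed concentrations (lognormal in the calculations), on the plain reading of SAP 8.2 and the Table 122 title, and on an assumed s. The simulations do not model values below the limit of detection. Given the exploratory purpose and the unknown s, the importance is minor to moderate.

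**What to change.** Make two changes together in SAP 8.2:

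1. Define the pre-first-vaccination value as the geometric mean of the two baseline concentrations, that is, the mean on the log2 scale.
2. Run the signed-rank tests of Tables 122 and 123 on log2 fold change, and retitle those tables to match.

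Keep the medians, bootstrap intervals and rank-sum tests, all on the same fold changes. For a 1.5-fold rise with between-subject SD 1.0, power goes from 74% to 86% at s = 0.3 and from 32% to 45% at s = 0.5.

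The cost is SAP wording, with no new data or tables. There are two drawbacks. Power to call falls in noisy analytes drops slightly (35% to 33% at s = 0.6, 25% to 21% at s = 0.8), because the present bias favours them. Values imputed at half the limit of detection also get more weight in the baseline: for illustration, values of 5 and 20 average to 12.5 arithmetically and 10 geometrically.

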9. TRANSCRIPTOMICS EVALUATIONS

The following sections describe the analysis of RNA-Seq endpoint data for the main Clinical Study Report. Analysis will be based on the PP analysis population. To the extent possible, transcriptomics analyses will be implemented using the R statistical programming language [1] and will utilize published R packages such as made available via the Bioconductor online resource [2]. At the start of the analysis, the most-up-to-date Bioconductor version, R statistical software, and other third-party software will be identified and used.

9.1. RNA-Seq Data Processing and Qc

9.1.1. Human Reference Genome Alignment and Quality Assessment

The latest version of the human reference genome assembly, gene models, and associated gene and transcript annotation information in the form of a Gene Transfer Format (GTF) file will be obtained from the ENSEMBL database [3]. Reference dataset versions will be documented in the CSR. Adapter sequences and low-quality 5' ending sequences will be removed from raw sequencing reads using the Trimmomatic software [4]. The impact of quality filtering will be assessed using FastQC software [5]. Quality-filtered reads will then be aligned to the reference transcriptome/genome using the latest version of HISAT2 splice-aware sequence aligner [6]. For each sample, the quality of reference alignments will be evaluated using the RSeQC software [7]. Quality measures for each laboratory will be summarized in tabular form, univariate boxplots and multivariate starplots (Figure 6).

9.1.2. Gene Expression Quantification and Data Normalization

Gene expression quantification will be carried out on the gene level using the featureCounts function of the Subread software [8]. Reads that overlap with multiple genes or map to multiple genomic locations on the reference genome will be excluded. Known ribosomal, transfer, and mitochondrial RNA genes will be removed from the final read count analysis dataset. In addition, genes located on the X and Y chromosomes will be excluded from the final read count analysis dataset to avoid gender-related biases.

Systematic sample differences in sequencing coverage will be corrected for by calculating scaling factors for each sample using the trimmed mean of M-values (TMM) method [9] as implemented in the edgeR software [10]. TMM-normalized moderated \log_2 counts per million (LCPM) for each gene will be calculated using the edgeR software [10]. As part of this step, a sequencing coverage-scaled count of 0.5 reads will be added to each gene to avoid taking the log of zero. LCPM distributions will be visualized using univariate boxplots and cumulative distribution function (CDF) plots before and after TMM-normalization.

